Christiana Care Hospital
Neurology Department

Study Protocol

Enhancement of Behavioral and Cognitive Outcomes in Autism Spectrum Disorder Via Neurostimulation

NCT05371912

Date: 7/21/2021

AIMS:

Aim 1: To determine the effects of High frequency (HF) repetitive Transcranial Magnetic Stimulation (rTMS) of the inferior parietal lobule (IPL) on social/behavior deficits in children and young adults with ASD.

Aim 2: To assess the differential effects of HF rTMS of the left versus right IPL on linguistic and visual coding abilities in ASD.

Aim 3: To evaluate the effects of right/left HF rTMS stimulation of IPL on executive functioning in ASD.

BACKGROUND:

ASD encompasses a wide range of impairments in the reciprocal social and communicative skills as well as presence of restrictive and/or repetitive patterns of behaviors. The environmental, genetic, and biological etiologies for ASD are yet to be fully defined. ASD is heterogeneous in nature and thus far, numerous genetic factors have been identified in the affected children, including single gene mutations, chromosomal abnormalities, and sub-microscopic deletions or duplications, altogether accounting for approximately 10% of cases. Some authors have predicted between 350 to 400 ASD susceptibility genes. Copy number variations are also found to play an important role in developing the ASD phenotype. Abnormalities in genes involved in epigenetic regulation, including mRNA translation, have been reported in ASD. Far less progress has been made in ascertaining the contribution of environmental factors in ASD.

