1. Children with ASD exhibiting significant anxiety or contact avoidance, precluding them from cooperating with the procedure
2. Children with a known diagnosis of seizures

INTERVENTION:

The rTMS treatment sessions will be scheduled 2 days a week for 5 weeks. In the beginning of each session, a single pulse stimulation will be utilized to determine the motor threshold. This is accomplished by increasing the intensity of the stimulation to achieve a twitch in the thenar muscle on the right hand. Eighty percent of the motor threshold will be applied for the treatment session. Each treatment session will consist of 10 minutes of HF rTMS delivery to the IPL, either the right or the left side, according to the paradigm detailed in the table below.

Frequency	10 Hz
Burst duration	10 seconds
Inter-burst intervals	20 seconds
Session time	10 minutes
Total stimulations per session	2000
Intensity	80% of motor threshold

The rTMS paradigm

rTMS TARGETING OF THE IPL:

For targeting the IPL, we are planning to use the standard 10/20 electrode placement system used for EEG recording. The IPL localizes to the Brodmann areas 7 and 40 and the P3/4 electrodes (15). A recent publication by Huang et al used sophisticated analysis of functional MRI and resting state functional connectivity in ASD and proposed multiple potential targets for neurostimulation including DLPFC, angular

gyrus and inferior frontal gyrus. Angular gyrus falls under Brodmann 40 and P3/4 EEG electric placement and overlaps with our proposed targeting of the IPL (16).

TREATMENT GROUPS AND THE EXPERIMENTAL DESIGN:

The patients will be randomized at the time of recruitment to either receiving left or right IPL stimulation. A standard shamming technique will be utilized to blind the patient regarding the treatment targeting (17). The neuropsychologist obtaining and interpreting the outcome measures will also be blinded. Only the clinician delivering the rTMS treatment will have a knowledge about the treatment targeting.

OUTCOME MEASURES:

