A battery of neuro psychological measures will be implemented at baseline, after completion of the rTMS intervention and three months later. To assure high quality and reproducibility of the results, the testing will be completed by an experienced and board-certified neuropsychologist at Nemours A.I. DuPont Hospital for Children. Also, to make certain of the validity and authenticity of the results, the psychologist will remain blinded regarding the hemispheric targeting of rTMS. The battery of tests will consist of the following elements:

NIHTB-CB – The NIH Toolbox of Neurological and Behavioral Functioning- Cognitive Battery was constructed to embody cognitive tasks that are influential in everyday functioning (18). The NIHTB-CB has been standardized for use with children and adults ages 3-85 years of age. Recent studies have demonstrated the NIHTB-CB as a reliable and valid assessment for both adult and pediatric individuals and consist of brief tasks which are administration via IPad Two of the tasks from the NIHTB-CB, Flanker and DCCS will be utilized to assess Executive Function (EF) as described below (19, 20).

Flanker: The Flanker Inhibitory Control and Attention is a test to measure the inhibitory and attentional facets of Executive Functioning. Administration of the Flanker task is approximately 4 -5 minutes and involves a central target (arrow or fish) flanked by two additional arrows on either side. The aim is to indicate the direction of the middle stimulus. Trials include either flankers facing the same direction (congruent) or distractor flankers that face the opposite direction from the middle stimulus (incongruent).

DCCS: The Dimensional Change Card Sort is a task designed to assess cognitive flexibility. The individuals are shown an on-target image and instructed to select one of two images matching the target based on the category of shape or color. Participants matched images by each dimension independently for 10 trials (5 trials shape matching and 5 color matching) followed by set of 30 “switch” trials. Raw scores are converted to normative standard scores (mean=100, SD=15) with higher scores indicating better performance.

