SRS-2: The Social Responsiveness Scale – Second Edition (SRS-2) is a 65-item, parent/caregiver-rated scale assessing social interaction and communication deficits (21). Different versions of the scale are used based on patient’s age and will be administered to parents. The total scale, which is the sum of responses (rated 1 to 4), is reported here. Raw scores range from 65 to 260 and are converted to t-scores (mean of 50 and standard deviation of 10). As such, higher scores suggest worse symptoms.

RRBs: Repetitive Behavior Scale-Revised is a parent rating scale that measures restricted repetitive behaviors (22). This scale consists of 43 items that correspond to six RRB subscales: stereotyped, self-injurious, compulsive, ritualistic, sameness, and restricted. Subscale scores are calculated by summing ratings (0=behavior does not occur to 3=behavior is a severe problem) of all correspondent items, representing the severity of each type of RRB. An overall RRB score is calculated by summing the subscale scores.

D-KEFS Verbal Fluency: The Delis-Kaplan Executive Function System (D-KEFS) Verbal Fluency task is composed of three subtests 2 of which will be implemented to quantify verbal fluency: Letter Fluency, Category Fluency, and Category-Switching Fluency (23). These subsets assess speed of generating words beginning with specified letters (Letter Fluency) or words from different categories (Category Fluency).

The final subtest evaluates cognitive set-shifting (an executive function) and verbal fluency. This test has alternate forms and is normed on individuals 8 years old through adulthood. Higher scores indicate more fluent word production.

WRAML-3: Design Learning subtest from Wide Range Assessment of Memory and Learning-Third Edition is a paper-and-pencil test with six subtests assessing immediate memory recall for participants aged 5-89 years (24). For this study, the Design Learning subtest will be used to assess immediate visual memory. In this task, the participant is shown a single card across four trials. The card has 18 different geometric shapes distributed across four quadrants. It is exposed for 10 seconds and then removed; after a 10 second delay the participant is asked to recall and draw the shapes in the correct locations. This procedure is repeated three times for a total of four trials.

NUMBER OF SUBJECTS:

This is a small pilot study which will include 20-30 subjects with ASD.

DURATION OF THE STUDY:

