We aim to recruit the subjects over a 2-year period. Each subject will receive the rTMS treatments 2 days a week for a period of 5 weeks and will be followed for three months after the intervention.

GENDER OF SUBJECTS:

There will be no gender preference when enrolling for this study.

AGE OF SUBJECTS:

We aim to recruit children and young adults with ASD. The subjects will be children 8 years or older and young adults up to 25 years old.

RACE & ETHNIC ORIGIN:

There will be no restrictions in enrollment based upon race or ethnic origin.

DATA ANALYSIS:

The numerical values generated by the above semi-quantitative measures (SRS, RRBs, NIHTB, DKEFS, WRAML-3) before and after treatment and after 3-moth follow up will be entered into an excel database and used for statistical analysis. For establishing statistical significance between the mean values before and after treatment, student t-test and confidence intervals will be used.

RISKS:

rTMS is a noninvasive method and not associated with any risks.

ADVERSE EVENTS:

The adverse effects of rTMS are mild and benign and consistent of transient headaches or scalp discomfort. Occurrence of seizures is quite rare; Krishnan et al. reported a total of 2 cases of seizures in 332 subjects participating in 35 trials of rTMS between 2004 and 2014. Both patients did have clear risk factors for seizures. These seizures occurred with the high-frequency stimulation of 15-20 Hz and short inter burst intervals which will be avoided in our protocol. Our study protocol will exclude all patients with history of epilepsy. Medications which may lower the seizure threshold will be avoided altogether if possible.

SEIZURE PROTOCOL:

If the patient should experience a seizure during the treatment, the following protocol will be followed

1. Universal seizure precautions and safety
2. Monitoring the vital signs

3. Calling the code and transferring the patient to the emergency room. If the seizure lasts for less than a minute, no specific treatments or interventions are necessary. However, the patient will be withdrawn from the study protocol. If the seizures are prolonged, in the emergency room, further decisions will be made regarding performing an EEG or other necessary treatments.

POTENTIAL BENEFITS TO THE SUBJECT AND SOCIETY:

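### Repeated performance tests with only a before/after t-test: practice gain would be counted as an rTMS effect for Aim 3 and any general improvement claim

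*Combined protocol and SAP*

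**What the plan says.** **Schedule.** OUTCOME MEASURES: "A battery of neuro psychological measures will be implemented at baseline, after completion of the rTMS intervention and three months later". DURATION OF THE STUDY adds that each subject is treated "for a period of 5 weeks and will be followed for three months after the intervention".

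**Tests.** For executive function, "Flanker and DCCS will be utilized to assess Executive Function (EF) as described below". For D-KEFS Verbal Fluency, "This test has alternate forms and is normed on individuals 8 years old through adulthood", but no form is assigned to any visit. For Design Learning, "In this task, the participant is shown a single card across four trials"; the card carries 18 shapes, and an alternate card is not mentioned. No practice session, repeat baseline or adjustment for practice is described for any test.

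**Arms.** TREATMENT GROUPS AND THE EXPERIMENTAL DESIGN: "The patients will be randomized at the time of recruitment to either receiving left or right IPL stimulation". Sham is described there only as a way to mask the side treated, not as a comparator arm.

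**Analysis.** DATA ANALYSIS: "For establishing statistical significance between the mean values before and after treatment, student t-test and confidence intervals will be used". No comparison between the arms is named, and pairing, sidedness and significance level are not stated.

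**Aims.** Aim 2 is "To assess the differential effects of HF rTMS of the left versus right IPL on linguistic and visual coding abilities in ASD". Aim 3 concerns the effect of right or left stimulation on executive functioning.

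**The concern.** The first retest comes at the end of the 5-week course, so whatever subjects gain from having met the tasks before falls in the same interval as the treatment. Every subject is stimulated, so no group shows what repetition alone would do. Blinding the neuropsychologist protects the scoring but does not stop the subject from learning.

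Design Learning is the clearest case. It is meant to measure immediate visual memory. If the same card is used at each visit, the subject has seen it 4 times before the post-treatment test and 8 times before follow-up, and 12 times in all. Later scores would then partly reflect retention. The documents do not say whether the card is reused, so these counts are conditional.

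What is at stake is the next step: POTENTIAL BENEFITS TO THE SUBJECT AND SOCIETY says that beneficial results would lead to a further grant application for a larger study. The parent-rated SRS-2 and Repetitive Behavior Scale are not performance tests and are outside this point.

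**Working it through.** The documents contain no power calculation, effect size or practice-effect estimate, so there is no figure of the plan's own to reproduce.

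**Inputs from the documents.** Three administrations; 5 weeks of treatment plus three months (35 + 91 = 126 days, about 4.1 months); 20-30 subjects in total; a standard-score scale with SD 15, given in the DCCS description.

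**Assumptions.** True rTMS effect zero; paired two-sided 5% t-test on all subjects; retest correlation r = 0.6 to 0.8; practice gain d = 0.1 to 0.5 in SD units, with equal SD at both visits; 1:1 allocation, so 10-15 per arm. On the SD-15 scale, 0.2 SD is 0.2 × 15 = 3 points.

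**Step 1: before/after test.** SD of change = √(2(1 − r)). Noncentrality = d / SD of change × √n. The chance of a significant improvement is the upper-tail rejection probability of the noncentral t with n − 1 degrees of freedom.

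- n = 20, r = 0.6, d = 0.2: SD of change = √0.8 = 0.894; noncentrality = 0.2 / 0.894 × √20 = 1.00; probability 15.6%.
- n = 30, r = 0.8, d = 0.2: SD of change = √0.4 = 0.632; noncentrality = 0.2 / 0.632 × √30 = 1.73; probability 38.8%.

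| Assumed gain | n=20, r=0.6 | n=20, r=0.8 | n=30, r=0.6 | n=30, r=0.8 |
|---|---|---|---|---|
| 0.1 SD | 6.9% | 9.9% | 8.6% | 13.1% |
| 0.2 SD | 15.6% | 26.9% | 21.9% | 38.8% |
| 0.3 SD | 29.6% | 52.1% | 42.7% | 70.9% |
| 0.5 SD | 66.0% | 91.8% | 84.1% | 98.7% |

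The nominal rate in this direction is 2.5%. These are rates per test.

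**Step 2: if the t-test is unpaired.** Ignoring the correlation makes the test conservative. By simulation (r 0.6-0.8, n 20-30), the upper-tail rate is about 0.5%-3.5% at a 0.2 SD gain and about 22%-47% at 0.5 SD. The mean change, and the centre of its confidence interval, is still shifted by the full gain.

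**Step 3: left-right difference in change.** If both arms gain d from practice, the expected difference in change is d − d = 0. In 40,000 simulated trials per setting (10 or 15 per arm, r = 0.7, d = 0.2 to 0.5), the two-sided false-positive rate was 4.9%-5.1%.

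**Step 4: precision of that comparison.** By the normal approximation with r = 0.7, the difference detectable with 80% power is (1.96 + 0.84) × √0.6 × √(2/n). That is 0.97 SD at 10 per arm and 0.79 SD at 15 per arm. Power for a 0.3 SD difference is 14%-18%.

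**The case against.** **Aim 2.** A reader might infer that practice gain undermines Aim 2 as it does Aim 3. The documents do not support that. Aim 2 asks about left versus right, subjects are randomised to side, and a shared gain cancels (step 3). What is missing for Aim 2 is a named between-arm test. This objection stands and limits the point.

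**Size of the gain.** The documents do not show that a practice gain will occur, how large it would be, or that it is greatest at the first retest. A reader might take the table as a forecast; it shows only what follows from each assumed gain. Pairing is also unstated, and an unpaired test shows little excess at 0.2 SD. This stands as to rejection rates, but it does not remove the shift in the mean.

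**Design Learning.** A reader might infer that learned shapes leave less room for a left-right difference. No maximum score, baseline level or retention rate is given, so this is not supported.

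**General cause.** Maturation, regression to the mean and medication tapering are equally inseparable from rTMS in a before/after comparison of two active arms. That is fair. Practice is still worth separate treatment, because part of it can be reduced by how the tests are given.

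**Pilot status and alternate forms.** The study calls itself a small pilot, and mentioning alternate forms may signal an intention to use them. No schedule says so, however, and forms for verbal fluency alone leave the other three tests uncovered.

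**Conclusion.** The point holds for Aim 3 and for any general claim of improvement on the four performance tests: under the plan as written, practice gain and rTMS effect cannot be told apart. For Aim 2 it holds only because DATA ANALYSIS names no comparison of the randomised arms.

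Under the stated assumptions and with a paired analysis, even a 0.1 SD gain raises the chance of a spurious improvement to about three to five times the nominal rate (6.9 / 2.5 = 2.8; 13.1 / 2.5 = 5.2). The practice gain and retest correlation are assumed. The bias in the estimated change equals the practice gain, whichever t-test is used. The change should be made before the before/after results are used to support a larger study.

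**What to change.** 1. In DATA ANALYSIS, for all four performance tests, make the left-right difference in change between the randomised arms the inferential comparison. Report before/after change with confidence intervals as descriptive, and state that it is not attributable to rTMS alone.
2. In OUTCOME MEASURES, assign the available D-KEFS alternate forms to visits in an order counterbalanced within each arm. The protocol does not say how many forms exist; if there are fewer than three, state which visits share a form. This limits memory for items, not general familiarity with the task.
3. Give Flanker and DCCS once, unscored, shortly before the scored baseline. This reduces the first practice step but does not remove it, so item 1 is still needed for these tests.
4. State whether the same Design Learning card is used at all three visits.

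**Cost.** A short amendment; a slightly longer baseline visit (the protocol puts Flanker at about 4-5 minutes, and DCCS is assumed similar); and a little noise from differences between D-KEFS forms. The main price is in what can be concluded: the between-arm comparison answers only left versus right, and with 10-15 per arm its precision is low (step 4). Whether rTMS improves these scores at all would remain unanswered by this pilot.

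### The examiner is masked to side but nothing hides the visit, so a general expectation of gain can enter the before-after estimate for examiner-scored tests, mainly Design Learning

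*Combined protocol and SAP*

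**What the plan says.** TREATMENT GROUPS AND THE EXPERIMENTAL DESIGN sets out two active arms: "The patients will be randomized at the time of recruitment to either receiving left or right IPL stimulation". A sham technique conceals from the patient which side is treated; no sham-only or untreated arm is described. The same section adds that "The neuropsychologist obtaining and interpreting the outcome measures will also be blinded", and OUTCOME MEASURES states what this covers: "the psychologist will remain blinded regarding the hemispheric targeting of rTMS".

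On timing, "A battery of neuro psychological measures will be implemented at baseline, after completion of the rTMS intervention and three months later". On who tests, "the testing will be completed by an experienced and board-certified neuropsychologist". No coded record, shuffled scoring order or separate scorer is described.

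On analysis, DATA ANALYSIS names one comparison: "For establishing statistical significance between the mean values before and after treatment, student t-test and confidence intervals will be used". It does not say whether the t-test is paired, or whether it is pooled over sides or run within each side.

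On the measures, Flanker and DCCS are given on an iPad, and SRS-2 and the Repetitive Behavior Scale are parent-rated. In Design Learning, a paper-and-pencil task, "the participant is asked to recall and draw the shapes in the correct locations". D-KEFS fluency asks for words by letter or category; how the responses are scored is not stated.

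**The concern.** The protocol presents masking of the psychologist as its guarantee of valid results. What is hidden is left versus right, while what is tested is before versus after. Because every subject is treated, an examiner who knows the visit also knows whether the subject has had rTMS. Expecting improvement after treatment could make borderline drawings score slightly higher at later visits. That shift would be added in full to the before-after difference and would look like a treatment effect. The section on potential benefits says that beneficial results would lead to a further grant application for a larger study, so a gain that came partly from scoring would carry forward.

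**Working it through.** The plan gives no alpha, effect size, SD or retest correlation, so it has no figure to reproduce. The check has two parts.

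**1. Which contrast does masking to side protect?** Let every post-treatment score carry a scoring shift *d* that does not depend on side, with no true effect.

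- Before-after, pooled: expected difference = *d*. The shift stays.
- Left-right difference in change: expected value = *d* − *d* = 0. The shift cancels.

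A simulation (40,000 runs; equal sides of 10 or 15, an assumption because the allocation ratio is not stated) agrees. Here the shift is in SDs of the change score.

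| Per side | Shift | Left-right test rejects | Pooled before-after test rejects |
|---|---|---|---|
| 10 | 0.3 | 4.9% | 24.9% |
| 10 | 0.5 | 4.9% | 56.6% |
| 15 | 0.3 | 4.8% | 35.7% |
| 15 | 0.5 | 4.9% | 75.4% |

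These shifts are large and serve only to show the mechanism.

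**2. How large could it be under more modest shifts?** Inputs:

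- *n* = 20 or 30, from NUMBER OF SUBJECTS.
- Assumed: two-sided 5% level, paired test pooled over sides, no true effect, shift *d* = 0.05 to 0.2 SD of the score, retest correlation *r* = 0.5 to 0.8.

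Formulas:

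- Shift in SDs of change: *d*z = *d* / √(2(1 − *r*))
- Noncentrality: λ = *d*z × √*n*
- False-positive rate = P(|T| > t(0.975, *n* − 1)), with T noncentral t on *n* − 1 degrees of freedom and noncentrality λ

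Worked case, *d* = 0.2, *r* = 0.7, *n* = 20: √(2 × 0.3) = 0.775; *d*z = 0.2/0.775 = 0.258; λ = 0.258 × √20 = 1.155; critical value 2.093; rate 19.5%.

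| *r* | *d* | *n* = 20 | *n* = 30 |
|---|---|---|---|
| 0.5 | 0.05 | 5.5% | 5.8% |
| 0.5 | 0.1 | 7.1% | 8.3% |
| 0.5 | 0.2 | 13.6% | 18.5% |
| 0.7 | 0.05 | 5.9% | 6.4% |
| 0.7 | 0.1 | 8.5% | 10.5% |
| 0.7 | 0.2 | 19.5% | 27.7% |
| 0.8 | 0.05 | 6.3% | 7.0% |
| 0.8 | 0.1 | 10.3% | 13.3% |
| 0.8 | 0.2 | 26.9% | 38.8% |

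If the test is run within each side (10 or 15 subjects) at *r* = 0.7, a 0.1 SD shift gives 6.6% or 7.5%. With *d* = 0, every rate returns to 5%.

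**The case against.** A reader might infer three stronger things, and the documents support none of them.

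- **That masking protects nothing in the analysis that is run.** This holds only for an expectation common to both sides. The background ties language to the left hemisphere and visual-spatial processing to the right. If the t-test is run by side, masking still blocks expectations of that kind.
- **That Aim 2 is compromised, because fluency and visual memory are its measures.** Aim 2 asks about left versus right, and masking to side is the right protection for that question. The missing between-side test in DATA ANALYSIS is a separate gap.
- **That the double-blind label is wrong.** Patient and neuropsychologist are both masked to targeting, and the protocol says so. The label is fair for the randomized contrast.

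Three further objections carry weight. First, the documents do not describe the scoring rules for either test, so how much room they leave for leniency cannot be seen. That Design Learning needs an examiner's judgement is a reasonable inference from a drawn response; for fluency the inference is weaker. Second, that the examiner knows the visit is inferred from silence, although one role does the testing throughout and nothing would conceal it. Third, the magnitude is assumption throughout, its lower end is negligible, and an unpaired test would give lower rates. It is also fair that, in a small uncontrolled before-after comparison, masked scoring removes only one of several sources of apparent gain.

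What survives is the mechanism: a general expectation of gain after treatment is not masked, and it falls on the one contrast that the plan tests.

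**Conclusion.** The point holds as a limited one. It concerns Design Learning chiefly and fluency possibly; it does not reach the iPad tasks or the parent ratings. Over the assumed range the false-positive rate runs from about 5.5% to 27% with 20 subjects and from 6% to 39% with 30. The range illustrates sensitivity and does not estimate actual bias: the shift, the correlation, the pairing and the pooling are all assumed. Scoring masked to visit is worth having because it is cheap, and it should be treated as an improvement and not as the repair of a fatal flaw.

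**What to change.** Before scoring starts, have study staff replace the subject and visit identifiers on the Design Learning sheets with codes. The same neuropsychologist then scores them in one batch at the end of follow-up, or in periodic batches of several subjects, in random order across subjects and visits. Do the same for fluency where a written transcript already exists. New audio recordings are not proposed: they would add identifiable data that the confidentiality section does not address. Because testing takes place at a different hospital from the one on the protocol's title, name who does the coding and holds the key.

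The cost is coding and shuffling 60 to 90 sets of sheets (3 visits × 20 to 30 subjects), with no extra rater or visit. Scoring is delayed, but the listed eligibility criteria do not use this test. Three limits remain: the examiner may recognise some responses, administration stays unmasked to visit, and practice, maturation and regression to the mean are untouched.

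### Aim 2 asks for the left-versus-right difference between the randomised arms, but the only contrast the analysis names is before versus after treatment

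*Combined protocol and SAP*

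**What the plan says.** The document is a combined protocol and SAP; there is no separate analysis plan.

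- **Aims, Aim 2:** "To assess the differential effects of HF rTMS of the left versus right IPL on linguistic and visual coding abilities in ASD".
- **Treatment Groups and the Experimental Design:** "The patients will be randomized at the time of recruitment to either receiving left or right IPL stimulation". Sham is used to conceal the side; no separate sham arm is described. The neuropsychologist is blinded, and "Only the clinician delivering the rTMS treatment will have a knowledge about the treatment targeting".
- **Outcome Measures:** the battery is given at baseline, after the intervention and three months later. The measures that appear to serve Aim 2 are D-KEFS Verbal Fluency, "composed of three subtests 2 of which will be implemented to quantify verbal fluency", and WRAML-3, of which the protocol says: "For this study, the Design Learning subtest will be used to assess immediate visual memory".
- **Number of Subjects:** "This is a small pilot study which will include 20-30 subjects with ASD". No sample-size calculation is given.
- **Data Analysis:** two sentences. One says what is entered for analysis: "The numerical values generated by the above semi-quantitative measures (SRS, RRBs, NIHTB, DKEFS, WRAML-3) before and after treatment", and again at three months. The other names the method: "For establishing statistical significance between the mean values before and after treatment, student t-test and confidence intervals will be used".

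**The concern.** Aim 2 concerns a difference between two groups. The named analysis concerns a change over time. The plan does not say whether the t-test is pooled or run by arm, and neither version yields the left-right difference unless a further step is added.

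The left-right contrast is the only comparison that randomisation and the assessor's blinding to side protect. Both arms receive active stimulation, so before/after change mixes any treatment effect with practice on repeated tests, maturation and expectancy. To the extent that these are common to both arms, they cancel in the left-right difference.

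If the contrast, score and time point stay open, they could be chosen after the data are seen. There is real room for choice: more than one fluency score and two post-treatment assessments.

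**Working it through.** **1. The text, side by side**

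| Element | What the plan gives |
|---|---|
| Question in Aim 2 | Left versus right |
| Randomised factor | Side (left or right IPL) |
| Contrast in Data Analysis | Mean before versus mean after treatment |
| Between-arm test, group-by-time term or other use of side | None in any section |

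Write L and R for the mean changes in the left and right arms. With equal arms, a pooled before/after test targets (L + R)/2, which carries no information on L − R. By-arm tests target L = 0 and R = 0 separately. Aim 2 needs L − R with its interval.

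**2. What the missing contrast could deliver**

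The plan states no power, alpha, effect size or SD, so it has no figure to reproduce. From the document: 20–30 patients in total. Assumed: 1:1 allocation (10 or 15 per arm), two-sided alpha 0.05, normal scores, no dropout, baseline/follow-up correlation r = 0.7 (range 0.5–0.8). Units are raw-score SDs, because the document gives no SD for the fluency or Design Learning scores.

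Approximate 95% half-widths at r = 0.7:

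- Change scores: t(2n−2) × √(2/n) × √(2(1−r)).
  - n = 10: 2.101 × 0.447 × 0.775 = 0.73
  - n = 15: 2.048 × 0.365 × 0.775 = 0.58
- ANCOVA: t(2n−3) × √(2/n) × √(1−r²).
  - n = 10: 2.110 × 0.447 × 0.714 = 0.67
  - n = 15: 2.052 × 0.365 × 0.714 = 0.54

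Simulation also allows for chance baseline imbalance, through SE = √[s²(1/n₁ + 1/n₂ + d²/Sxx)], where d is the baseline difference between arms and Sxx the within-arm baseline sum of squares, with n₁ + n₂ − 3 degrees of freedom. It gives:

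| | 10 per arm | 15 per arm |
|---|---|---|
| ANCOVA mean half-width, r = 0.7 (r = 0.5 to 0.8) | 0.68 (0.83 to 0.57) | 0.54 (0.66 to 0.45) |
| Change-score mean half-width, r = 0.7 | 0.72 | 0.57 |
| ANCOVA power for 0.5 SD, r = 0.7 (r = 0.5 to 0.8) | 30% (22% to 40%) | 44% (32% to 58%) |
| Change-score power for 0.5 SD, r = 0.7 | 28% | 40% |
| Detectable with 80% power, ANCOVA, r = 0.7 | 0.98 SD | 0.77 SD |

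ANCOVA narrows the interval by about 5%–6% at r = 0.7. Over r = 0.8 to 0.5 the gain is 2%–10% with 10 per arm and 3%–12% with 15.

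Sensitivity at r = 0.7, ANCOVA: with 8 completers per arm, half-width 0.79 SD and power 24%; with a 7/13 split of 20 patients, 0.72 SD and 28%.

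**3. Why two within-arm tests are no substitute (illustration)**

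The plan does not say that within-arm p-values will be compared. If they were, and both arms truly changed by the same amount, the chance that exactly one arm is significant is 2p(1−p), where p is the power of the paired t-test in one arm. At a common change of 0.5 SD of the change score (0.5 × √0.6 = 0.39 raw SD at r = 0.7):

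- n = 10: p = 0.293, so 2 × 0.293 × 0.707 = 41%
- n = 15: p = 0.438, so 2 × 0.438 × 0.562 = 49%

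The result depends on the size of the common change:

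| Common change (SD of change) | 0 | 0.3 | 0.5 | 0.8 | 1.0 |
|---|---|---|---|---|---|
| 10 per arm | 10% | 24% | 41% | 47% | 32% |
| 15 per arm | 10% | 31% | 49% | 29% | 10% |

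A direct between-arm test would wrongly find a difference about 5% of the time.

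**The case against.** The strongest reply is that this is a wording gap in a small pilot. The outcomes will be collected at all three time points, the arms are randomised, and a left-right difference with an interval can be derived from by-arm results. A two-sample t-test on change scores, close to what is already named, would close the gap, and the preference for ANCOVA rests on a small gain. The pilot claims no power and could say little about side in any case.

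Much of this stands. No data are lost, change scores are an acceptable alternative, and post-hoc choice of contrast is a risk and not a certainty. The outcome list in Data Analysis omits side, but it does not claim to list every database field, so little weight falls on that. The protocol's intention to seek funding for a larger study says nothing about choosing a side; that a left-right estimate would help there is an inference. The power figures depend heavily on the assumed correlation.

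It does not remove the point. The t-test is tied expressly to means before and after treatment, so a between-arm test cannot be read into it. Pilot status excuses low power, not the absence of an analysis for one of three stated aims.

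**Conclusion.** The concern holds and should be fixed before any outcome data are analysed. The named analysis does not answer Aim 2, and no other section supplies the contrast. This rests on the text alone and needs none of the numerical assumptions.

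The numbers show only what the added contrast can deliver. Under the assumptions listed, an interval of roughly ±0.5 to ±0.7 SD at r = 0.7 makes it estimation: a null result could not rule out a moderate difference between sides. Two limits apply. Linking Aim 2 to D-KEFS Verbal Fluency and WRAML-3 Design Learning is inferred from their descriptions. Aim 3 is ambiguous about whether it compares sides, and the finding does not rely on it.

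**What to change.** Keep the before/after analysis for Aim 1, stated as a paired t-test with 95% CI and with the caveat that both arms receive active stimulation. For Aim 2, add text such as:

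> The left-minus-right difference in follow-up score, adjusted for baseline by ANCOVA, will be estimated with a 95% CI at end of treatment (main) and at 3 months (supportive), for one D-KEFS verbal-fluency score named in advance and for WRAML-3 Design Learning. The number analysed per arm will be reported. Within-arm p-values will not be compared to infer a side difference. This is pilot estimation without multiplicity adjustment. Side will be added to the analysis file by subject number after outcome scoring is complete, so that the assessor stays blinded.

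A two-sample comparison of change scores would also close the gap, with slightly wider intervals. The sponsor should confirm which measures serve Aim 2, and should apply the same model to Flanker and DCCS only if Aim 3 is meant to be comparative.

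The cost is a few sentences and one column in the analysis file, with no new visits, tests or patients. Because only the treating clinician knows the side, the plan must state how and when it is released. The downside is wide intervals, wider still with dropout.
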